10.4.2 Exacerbations history at baseline

Participants will be asked how many COPD exacerbations they have experienced in the last 12 months and whether any of those required hospital care.

10.4.3 Exacerbations record during the trial

Participant reported and recall of exacerbation events are highly reliable.^{47,48,49} Exacerbations will be participant reported throughout the trial (not tied to scheduled visits) and dates determined to the nearest calendar day. Participants will be advised how to report/notify the local trial team of their exacerbation details as they happen for an event. A participant COPD exacerbation diary card will also be provided to enable participants to record the details of each exacerbation. At scheduled visits, exacerbations information will also be collected, and details confirmed or corroborated if needed.

Participants' relative/next of kin/healthcare team can also contact the trial team if needed to let them know of the exacerbation if the participant is too unwell.

If a participant has 3 or more exacerbations per a year period from starting their trial medication, the trial team will review this information to see if the trial medication stopping threshold is met and if the IMP should be discontinued. If so, the participant and their healthcare provider will be informed so they can decide if the participant should restart their routine clinical care azithromycin prescription.

Further information on the IMP stopping rule and treatment of exacerbations and infections during the trial whilst on IMP are provided in sections 8.7 and 8.8 respectively.

10.4.4 Exacerbation within period from randomisation to receipt of trial medication

There will likely be a short delay from the time of randomisation to receipt of trial medication since trial medication will be home delivered. All participants will be advised to remain on their current clinical prescription of azithromycin until receipt of trial medication and then to start trial medication. If a participant exacerbates prior to receipt of trial medication it is likely this will be similar across all three treatment arms.

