8.6 Participant Withdrawal Criteria

Each participant has the right to withdraw from the trial at any time. The reason(s) for withdrawal will be recorded on the CRF if this is possible to do so. Although, there is no obligation for participants to provide a reason.

It is always within the remit of the physician responsible for a participant to withdraw a participant from a trial for appropriate medical reasons. Participants may be withdrawn from trial treatment for any of the following reasons as examples:

- 3 or more exacerbations/year
- Unacceptable adverse effects
- Development of serious disease preventing further treatment, or any change in the participant's condition that justifies discontinuation of trial treatment in the clinician's opinion
- Exacerbation in time period from randomisation to receipt of trial medication (home delivered from central pharmacy).

If participants are withdrawn from trial treatment or a participant wishes to stop trial treatment, they will be asked whether they would be willing to remain in scheduled trial follow-up, or if they do not want this, if they allow routinely collected clinical data (i.e. hospital admissions records and mortality) to be used for trial follow-up purposes.

If a participant decides to withdraw from the trial, any data already collected or results from tests already performed will continue to be used in the trial analysis unless explicitly requested by the participant for destruction. The participant should be asked if they would consent to routinely collected healthcare information (for example hospital admissions) to be used for trial purposes until the end of the trial.

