10.5.2 Week 1 (+ 14 /- 7 days) telephone call

- Confirm participant is content to continue to participate in the trial.
- To check received trial medication, understands how to take it and date when started trial medication and check trial medication compliance.
- Assessment of AEs and SAEs. Please see sections 11.4 and 11.5.
- 10.5.3 Telephone follow-up (3, 6 months (+/- 14 days))
- Confirm participant is content to continue to participate in the trial.
- Record any exacerbations details/confirmations; if information regarding exacerbations has already been provided. Healthcare usage.
- Questionnaires
 - CAT score
 - Cough VAS (6 months only)
- Check trial medication compliance-if still on trial medication
- Assessment of adverse events and SAEs. Please see sections 11.4 and 11.5

10.5.4 Visits follow-up (12 months (+/- 14 days), and ~6 monthly (alternate visit or telephone) until end of trial)

- Confirm participant is content to continue to participate in the trial.
- Check smoking status (every 12 months)
- Record any exacerbations details/confirmations; if information regarding exacerbations has already been provided. Healthcare usage.
- Questionnaires
 - CAT score, (every 6 months)
 - Cough VAS, EQ-5D-5L (every 12 months)
- Check trial medication compliance if still on trial medication
- Assessment of adverse events and SAEs. Please see sections 11.4 and 11.5
- SWAP end of trial: SHS, CFS, data to enable calculation of eFI and Cambridge multimorbidity score

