15 STATISTICS

15.1 Statistical Methods

A Statistical Analysis Plan (SAP) will be written and approved by the TSC and NIHR. A version of the SAP outlining the key aspects of the primary analysis, will be produced before any efficacy data is examined by the independent data monitoring committee (iDMC), TSC, or any members of the trial team. An interim SAP will be produced before any interim analysis is performed.

The primary endpoint is time to first exacerbation. The experimental treatments are complete discontinuation, seasonal discontinuation, and the control arm is continued azithromycin (this is standard of care). The hazard ratio comparing the two experimental arms to control will be estimated using a Cox proportional hazards model, adjusting for pre-randomisation factors of exacerbations history (number in preceding 12 months) and recruitment site. The consensus decision of the project team was that recruitment site and history of previous exacerbations (given this is the strongest predictor of exacerbations) are appropriate pre-specified covariates. Formal inference will compare the 1-sided confidence interval to the non-inferiority margin of a hazard ratio of 1.25. If the interval lies entirely below 1.25 then a conclusion of non-inferiority will be made. The confidence intervals will be at a 97.3% level, to adjust for there being two comparisons, and thus preserve an overall 5% significance level. The primary analysis will be an Intention to Treat analysis.

For the panel of subgroup factors to consider (section 15.1.1-15.1.2), the analysis will estimate the main effect and a treatment-subgroup interaction on the hazard ratio scale, adjusting for baseline covariates used in the primary analysis. This will be carried out in a univariate fashion, looking at each subgroup individually. Potentially, a multivariate model will be developed to include multiple subgroups simultaneously and provide a risk score. Standard 95% confidence intervals for the estimated subgroup-treatment interaction hazard ratio will be the primary focus. Multiple testing would preclude making strong claims of formal statistical significance; and any personalised treatment strategy would need to be validated in future research.

Secondary endpoints will be analysed using a similar regression methodology, as suitable for the nature of the endpoint (binary, categorical, continuous, time-to-event). The rate of

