15.3 Participant Numbers

This is an event-driven, non-inferiority trial, where the sample size and duration of follow-up is dependent on the number of primary endpoint (time to first exacerbation) events that occur. Estimation of the number of events required and therefore modelling of sample size required to achieve this number of events is based on available evidence.

Assuming a median time to first exacerbation (TTFE) of 150 days^{4,9,43} in the control standard of care arm (continuous treatment), and a non-inferiority threshold of 30 days, equates to the threshold on the hazard ratio scale of 1.25. The non-inferiority threshold of 30 days selected, was judged by respiratory specialists to be a clinically relevant margin of TTFE. There are no validated minimum clinically important differences for COPD exacerbations, including time free or until a COPD exacerbation. Given that a 2-week window between exacerbations is often used to define separate events,⁴⁶ TTFEs reviewed in azithromycin trials,^{4,9,43} as well as TTFE in a large non-inferiority COPD treatment trial (FLAME trial),⁶⁴ all support 30 days as a reasonable non-inferiority margin.

Sample size is based on 90% power for two non-inferiority comparisons (seasonal and placebo compared with continuous as standard treatment), at 2.7% significance (Dunnett test for multiple comparisons) using a Cox proportional hazards model. The number of primary endpoints required is **1242**. We assume a recruitment rate of ~560-630 participants per year,^{48,50} and a recruitment period of 29 months.

The total **sample size** estimate is thus **1311 (n=437 per arm)** and allows for $\sim 5\%$ dropout before the primary endpoint (first exacerbation), or censoring, to achieve the required 1242 events.

Data from previous withdrawal trials of corticosteroids^{65,66} suggest that adverse events (COPD exacerbations predominantly) was the main reason for dropouts. Given that our primary endpoint is TTFE, and that the expected median time to the primary event is approximately 5 months, only a tiny number of dropouts should happen before the primary event occurs. The anticipated median follow-up period of 24 months for the trial cohort is

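### Exacerbations before trial medication arrives are set aside as similar across arms, but in this non-inferiority test that similarity tilts the result modestly towards a non-inferiority claim

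*Protocol*

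**What the plan says.** Protocol section 10.4.4 expects a delay of unstated length between randomisation and home delivery. Everyone takes their own azithromycin until delivery. On exacerbations in that interval it says: "If a participant exacerbates prior to receipt of trial medication it is likely this will be similar across all three treatment arms".

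Section 8.6 lists the same event among its example reasons for withdrawal from trial treatment: "Exacerbation in time period from randomisation to receipt of trial medication (home delivered from central pharmacy".

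Section 15.1 sets the test. "The primary analysis will be an Intention to Treat analysis". "Formal inference will compare the 1-sided confidence interval to the non-inferiority margin of a hazard ratio of 1.25", and "If the interval lies entirely below 1.25 then a conclusion of non-inferiority will be made". On the level: "The confidence intervals will be at a 97.3% level, to adjust for there being two comparisons". Section 15.3 sizes the trial "at 2.7% significance (Dunnett test for multiple comparisons) using a Cox proportional hazards model".

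Section 15.5 censors participants who withdraw fully, or finish follow-up, without a first exacerbation. Someone who exacerbates in the gap is in neither group. No section excludes such an event from the primary endpoint, and no section states that endpoint's time origin. Randomisation is given as the starting date only for survival (section 13.1.2).

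The week-1 call records the "date when started trial medication" (section 10.5.2). Its window ends at day 14 in section 10.5 and at day 21 in section 10.5.2.

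**The concern.** Balance across arms is a comfort in a superiority trial, where events under identical treatment only make a difference harder to show. In a non-inferiority trial the direction reverses. The endpoint is the first exacerbation, so each participant supplies at most one primary event. If it falls in the gap, it is observed while all three arms take azithromycin and the true ratio is 1. Averaging such events with those after the switch moves the estimate towards 1, the side on which non-inferiority is declared.

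At stake is the error rate of the decision rule. A discontinuation strategy whose true effect sits at the margin once treatment differs would pass more often than the 2.7% per comparison that the design allows. Section 10.4.4 does not merely leave this to the SAP: it gives a reason for setting the matter aside, and that reason does not hold for this test.

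**Working it through.** **Inputs (Protocol sections 7.1, 15.1 and 15.3).** Margin 1.25; one-sided 2.7% per comparison; 90% power; 1242 events over three arms; 1311 randomised 1:1:1; control median 150 days. The delay is not given, so 7, 14 and 21 days are assumptions.

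**1. Reproduce the event target.** Events for one pairwise comparison, 1:1: 4 × (1.927 + 1.282)² / (ln 1.25)² = 827 (Schoenfeld, true ratio 1). Half, rounded up, is 414 per arm, and 3 × 414 = 1242, the stated figure. Each comparison then uses 828 events.

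**2. The pass mark.** SE of the log hazard ratio = √(4/828) = 0.0695. Non-inferiority needs an estimated log ratio below 0.2231 − 1.927 × 0.0695 = 0.0892, a hazard ratio below about 1.093.

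**3. Dilution.** With a constant hazard of ln 2/150 per day, the share with a first exacerbation within d days is f = 1 − 2^(−d/150). Taking a ratio of 1 before receipt and 1.25 after, the average log ratio is about (1 − f) × ln 1.25, and the false non-inferiority rate is Φ((0.0892 − average log ratio)/0.0695).

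| Gap, all participants | f (of 1311) | Average HR | False non-inferiority, one comparison | At least one false claim, both arms at the margin |
|---|---|---|---|---|
| 0 days | 0 | 1.250 | 2.7% | 4.9% |
| 7 days | 3.2% (42) | 1.241 | 3.4% | 6.1% |
| 14 days | 6.3% (82) | 1.233 | 4.2% | 7.5% |
| 21 days | 9.2% (121) | 1.225 | 5.2% | 9.0% |

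The last column uses a correlation of 0.5 between the two comparisons, from the shared control arm.

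**4. Simulation.** 20,000 two-arm Cox analyses per scenario, 437 per arm, gave 2.9% with no delay, then 3.5%, 4.2% and 5.3% at 7, 14 and 21 days. Delays spread uniformly over 0-14 days gave 3.5%, and over 0-21 days 3.8%. The simulation error of a rate near 3% is about √(0.03 × 0.97/20,000) = 0.12 percentage points.

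**5. Sensitivity to the early hazard.** Section 8.1 requires at least six weeks without an exacerbation, so the hazard just after entry may be below average. With an assumed 300-day median in the gap, 7 days gives f = 1 − 2^(−7/300) = 1.6% and a rate of Φ(−1.927 + 0.016 × 0.2231 × √207) = Φ(−1.876), about 3.0%. A higher early hazard would work the other way.

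**6. Clock started at receipt.** With a 21-day gap for everyone and participants with earlier events left out, the simulation returned a hazard ratio of 1.251 and a false non-inferiority rate of 2.8%, in line with no delay.

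**The case against.** Four arguments carry weight.

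- **Premise.** That gap events count is inferred. With no time origin stated, the SAP, which is not at hand, may begin the clock elsewhere or add other analysis sets. This stands as a limit: a reader might infer that intention to treat is the only analysis planned, but the protocol says only that it is primary and is silent on others. What remains is the reason given in section 10.4.4 and a decision rule that names no second analysis.
- **Size.** A reader might infer that the error rate nearly doubles. That needs every participant to wait about 21 days, the outer edge of a telephone window and not a delivery time; section 10.5 ends the same window at day 14. Section 10.4.4 expects the delay to be short, and section 9.1.1.2 has supplies sent by courier or post. Nor is the ratio drawn down to 1: it moves from 1.25 to between 1.24 and 1.22. Both corrections stand.
- **Target of estimation.** For the effect from randomisation in a pragmatic trial, gap included, the 2.7% is kept. That is formally right, and it is why intention to treat should remain. But section 15.3 derives the margin from 150 against 120 days (150/120 = 1.25), with no allowance for a period of common treatment, and the gap is a matter of trial supply rather than part of a discontinuation strategy.
- **Remedy.** An added analysis censoring at the end of trial medication would bring possible informative censoring and is not needed here. The stopping threshold of three exacerbations acts after the primary event, so it gives no reason for that censoring. Replacing the randomisation clock outright is also debatable and unnecessary.

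**Conclusion.** The point holds in a moderate form. The reassurance in section 10.4.4 is wrong for a non-inferiority test: events under identical treatment favour a non-inferiority claim, and the protocol states nothing that offsets this. The distortion of the hazard ratio is slight. The false non-inferiority rate per comparison rises from 2.7% to about 3.4%, 4.2% or 5.2% for a uniform gap of 7, 14 or 21 days, and to about 3.5% to 3.8% if delays are spread over two or three weeks.

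These figures assume that gap events count as primary events, a constant hazard from randomisation with the 150-day median, and an immediate change to a ratio of 1.25 at receipt. For the seasonal arm, a constant ratio after receipt is a simplification. The actual delay is unknown. A lower hazard soon after a stable period would shrink the effect; none of the assumptions reverses its direction. The change is worth making because it is cheap, not because the design fails without it.

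**What to change.** 1. Remove the reassurance from section 10.4.4 and say how exacerbations before receipt are handled.
2. State the time origin of the primary endpoint in section 15.1.
3. Keep intention to treat from randomisation. Pre-specify a paired analysis in participants who start blinded trial medication, counting the first exacerbation after the first dose. Claim non-inferiority only if the one-sided 97.3% bound is below 1.25 in both.
4. Say how someone who exacerbates in the gap and then starts trial medication enters the paired analysis, using the existing two-week separation rule (section 10.4.1). The simulation of the receipt clock left such participants out.
5. Reconcile the week-1 call windows in sections 10.5 and 10.5.2.

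The start date is already collected. Treatment before the first dose is the same in all arms and dispensed supply is blinded, so restricting to starters should leave the arms comparable.

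**Cost.** Wording, plus some precision. A 7-day gap removes about 3% of events from the paired analysis. If all 21-day events were lost and not replaced, 828 × (1 − 0.092) ≈ 752 remain and power is Φ(0.2231 × √(752/4) − 1.927) = Φ(1.13), about 87% instead of 90%. Joint power for passing both analyses has not been computed; it cannot exceed the lower of the two and should be checked once a realistic delay is known.

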10.4.5 Data collected from healthcare records

If available, specific data from participant's healthcare records relevant to this trial's objectives will be recorded in the CRF at baseline visit. These data will also likely be participant reported and where possible data will be corroborated from the participant with the healthcare records.

Data collection from healthcare records and/or participant reported that will be recorded at baseline include:

- Demographics (age, sex, ethnicity) and contact details
- Exacerbations history (in previous 12 months)
- Medical history including cardiovascular disease history and comorbidities
- Smoking history/status, i.e. current or ex-smoker
- Drug/medications including azithromycin duration of use and current prescription
- Most recent eosinophil blood count, historic highest and lowest eosinophil blood count (\leq 3 years)
- Information from computerised tomography (CT) of the chest (most recent), if available.
- Spirometry result if available (for example, FEV₁ (L)/FEV₁ %, FEV₁/FVC)
- Sputum result if available (≤ 12 months)-if positive culture.(Please see TPM).

10.4.6 Sputum result

Sputum testing will be performed as part of routine standard of care and is not a trial assessment. If a sample is clinically indicated and sent to local lab via routine clinical care during the trial, the result will be recorded in the trial only if it is culture positive and if so, the most recent sample to the visit date will be recorded if multiple positive samples are available.

10.4.7 Height, weight and BMI

Where possible height and weight measurements will be carried out using weighing scales and a wall height chart/stadiometer. If this is not possible, height and weight will be obtained from patient recall or medical records. BMI will be calculated from the height and weight.

10.4.8 Blood test

The full blood count (FBC) at baseline will be obtained (~4 mls) unless there is one available from the last six months. It is recognised there can be a delay in organising a separate blood test appointment if unable to do within baseline visit. This will not delay the participant starting trial medication and this information will be recorded. It is recognised this assessment is also dependent on impact of COVID-19 pandemic situation at the time of the trial.

10.4.9 Spirometry

Basic spirometry may be performed at baseline unless there is a most recent spirometry result in the records from the last 2 years. Spirometry will be performed in accordance with local standard of care practice/standard operating procedures (including GP practices if able to do).⁵⁰ Post bronchodilator lung function will be used. If a participant is unable to perform spirometry, it will not preclude them from participating in the trial, and scheduling a separate appointment for spirometry should not delay the participant starting trial medication and this information will be recorded.

Questionnaires

Individually, each questionnaire should only take a few minutes to complete, but may take up to 20 minutes to complete in total. The questionnaires have been selected for their ease and simplicity of use and/or are validated assessments used in clinical care and/or research.

10.4.10 Health related quality of life (EQ-5D-5L) (approximately 2 mins)

Health related quality of life data will be captured at baseline, and during trial follow-up. Assessments will be undertaken using EuroQoL 5D-5L (EQ-5D-5L) Index that has been used widely in COPD. EQ-5D-5L was developed as a utility questionnaire and addresses mobility, self-care, usual activities, pain/discomfort and anxiety/depression. The completed instrument can be translated into quality-of-life utilities suitable for calculation of QALYs through the published UK tariffs.⁵¹

10.4.11 COPD Assessment Tool (CAT) (approximately 5 mins)

CAT will be assessed at baseline and during trial follow-up. This is a validated short (8 questions) simple patient completed questionnaire, with good discriminant properties, developed for use in routine clinical practice to measure the health status of patients with COPD. Despite the small number of component items, it covers a broad range of effects of COPD on patients' health. Studies have shown that it is responsive to change and to treatment.⁵²

It takes a few minutes to complete and can be completed on paper or online via the CAT website. The result can be either saved and emailed or printed out.

10.4.12 Cough visual analogue scale (VAS) (approximately 1 min)

Cough VAS (0-100mm) will be assessed at baseline and during trial follow-up. It is a simple, quick patient completed assessment of cough used to assess cough severity in patients with chronic cough, whereby patients mark from 'no cough' (0mm) to 'worse cough ever' (100mm) on a linear scale. Cough VAS scale is highly repeatable over a 2-week period in patients with cough due to COPD.⁵³

10.4.13 Frequent productive cough (approximately 2 mins)

The presence of frequent productive cough (symptoms associated with chronic bronchitis) will be assessed at the baseline visit by questionnaire - from the two questions on cough in

the CAT score (10.4.12) and two questions on cough from the St George's Respiratory Questionnaire (SGRQ)-COPD.^{54,55} Further information will be provided in the TPM.

10.4.14 Patient health questionnaire-2 (PHQ-2)- depression screen (approximately 2 mins)

This component will be used to screen for depression at baseline and comprises the first 2 items of the PHQ-9 assessment. It is based on recall over the last two weeks and is scored from 0-6. A higher score indicates increased likelihood of a depressive disorder and need of further investigation. A score of 2 or higher may suggest a possible depressive disorder. The PHQ-2 has been validated in many studies and has shown sensitivity of 83% and specificity of 92%. It is often used in primary care to screen for depression and is quick and easy for patients to fill out.⁵⁶ If the PHQ-2 screening test is suggestive of a possible depressive disorder and this is not already a known diagnosis, the participant will be advised to see their GP about it. Any clinically relevant findings from trial participant that are deemed to require follow-up will be communicated to the GP. Please refer to the TPM.

10.4.15 Generalised Anxiety Disorder-2 (GAD-2)- anxiety screen (approximately 2 mins):

This is a 2-item instrument that is used to screen for anxiety and will be used at baseline. It is often used in primary care as it is simple and easy to do. It comprises the first 2 items of the GAD-7 questionnaire. It is scored from 0-6 with a higher score indicating an underlying anxiety disorder. A score \geq 3 is suggestive of an underlying anxiety disorder and need for further investigation. The GAD-2 has been validated in many studies and has reasonable sensitivity of 83% and specificity of 92% similar to the GAD-7.⁵⁷ If the GAD-2 screening test is suggestive of a possible anxiety disorder and this is not already a known diagnosis, the participant will be advised to see their GP about it. Please refer to the TPM.

10.4.16 Healthcare usage

Information regarding healthcare usage (hospitalisation and primary care consultations for example) will be recorded.

10.4.17 Adherence

Adherence will be evaluated during trial follow-up by estimated compliance, whereby participants will be asked to return trial bottles and unused medication to the trial research team at their appointment(s).

10.4.18 Adverse events/SAEs

Adverse events (AEs) and SAEs will be assessed at baseline and during trial follow-up. AEs will be recorded within the medical notes; SAEs will be reported to the central OPACE trial team for CI review. For more information see section 11.

10.4.19 Self-Rated Health Status (SHS) (approximately 1 min)

This will be assessed at baseline and at the end of trial and will be used in the Study Within a Project (SWAP) as described in the Appendix B. The SHS is a one question assessment of health status recommended by NICE as a screening tool for frailty in patients. It asks patients to rate their health on a scale of 0-10. A score of 6 or less indicates frailty.^{19, 58}

10.4.20 Clinical Frailty Scale (CFS) (approximately 1 min)

This will be assessed at baseline and end of the trial as part of the SWAP as described in Appendix B. The Clinical Frailty Scale (CFS) is a tool used in clinical practice in older patients to provide an assessment of capability (in last two weeks) which may be helpful to indicate frailty. It can be conducted by any appropriately trained healthcare professional.⁵⁹

10.4.21 Electronic Frailty Index (eFI) (approximately 2 min):

This forms part of the SWAP (Appendix B) and will be calculated at baseline and end of trial if this is possible and sufficient data recorded to enable this. The electronic frailty index (eFI) uses existing information from the local healthcare record and is recommended by NHS England to be used as a tool to indicate frailty. The eFI is based on 36 deficits and is calculated based on the sum of deficits an individual may have/total number of deficits (i.e. 36).^{60, 61} It can be calculated by software automatically from read codes in the primary healthcare record and it is recommended for GPs to do this. Whether sites will be able to easily have access to a participant's eFI is unknown, and it will be calculated based on data entered into the trial database, if sufficient data is recorded to enable this.

10.4.22 Cambridge MultiMorbidity Score (CMMS) (approximately 1 min)

This forms part of the SWAP (Appendix B) and will be calculated at baseline and end of trial if this is possible and sufficient data recorded to enable this. The Cambridge Multimorbidity score (simplified version based on 20 weighted conditions) has been validated to predict key health outcomes based on morbidities. It will be calculated based on data entered into the trial database, if sufficient data is recorded to enable this.⁶²

Questionnaires/data collected from 10.4.19-10.4.22 is for the SWAP (study within a project) - see Appendix B.

